#### 1.3.4.2. Study AI444-040 Preliminary Efficacy

In the genotype 1 HCV treatment groups, 100% of patients achieved SVR through post-treatment week 4 (SVR4) irrespective of whether RBV was or was not administered. In the genotype 2 and 3 treatment groups, 91% (40/44) of patients achieved SVR4. Two patients with HCV GT-2 infection who received DCV+GS-7977+RBV discontinued the study for non-AE-related reasons and were lost to follow-up. Two patients with HCV GT-3 infection who received GS-7977+DCV experienced virologic failure: one had viral relapse and the other met the protocol definition of viral breakthrough (confirmed HCV RNA >LOQ on or after Week 8).

On-treatment HCV RNA data are tabulated in [Table 1-6](#).

**Table 1-6. The Proportions of Patients Achieving Viral Load Below the Lower Limit of Quantification (HCV RNA < 25 IU/mL) in Study AI444-040**

Dose	HCV Genotype	Week 4 On-Treatment	Week 12 On-Treatment	Week 24 On-Treatment	Week 4 Post-Treatment (SVR4) a
7-day lead-in dose of GS-7977, then GS-7977 + DCV for 23 weeks	GT 1	100% (15/15)	100% (15/15)	100% (15/15)	100% (15/15)
	GT 2/3	100% (16/16)	88% (14/16)	94% (15/16)	88% (14/16) b
GS-7977 + DCV for 24 weeks	GT 1	100% (14/14)	93% (13/14) c	86% (12/14) c	100% (14/14)
	GT 2/3	100% (14/14)	93% (13/14)	100% (14/14)	100% (14/14)
GS-7977 + DCV + RBV for 24 weeks	GT 1	100% (15/15)	100% (15/15)	93% (14/15) c	100% (15/15)
	GT 2/3	100% (14/14)	100% (14/14)	86% (12/14)	86% (12/14) d

- a In this study, SVR4 was defined as viral load below the lower limit of quantification. All but one patient who achieved SVR4 also had detectable viral load (HCV RNA <10 IU/mL); this patient had undetectable viral load when retested eight days later.
- b One patient experienced viral relapse and one patient experienced viral breakthrough.
- c Percentages less than 100% reflect missing values.
- d Two patients were lost to follow-up.

### 1.3.5. Study P2938-0721 QUANTUM

Two hundred thirty-nine (N=239) treatment-naïve patients with chronic HCV with or without cirrhosis were randomized to receive 12 (Groups A, B, C, D) or 24 weeks (E, F, G, H) of GS-0938 (Arms A, E), GS-0938+GS-7977 (Groups B, F), GS-7977+ RBV (Groups C, G), and GS-0938+GS-7977+RBV (Group D and H). Group I is a deferred start group (placebo) for 24 weeks. Approximately 25 patients per group were enrolled. GS-7977 was administered at a dose of 400 mg QD. GS-0938 was administered at a dose of 300 mg once-daily (QD). The RBV dose was 1200 mg or 1000 mg per day in divided (BID) doses, as determined by subject's weight (e.g., ≥ or < 75 kg).

Due to a safety signal (ALT elevations) sites were instructed, to immediately discontinue all study medications in all subjects who had been exposed to GS-0938 (Groups A, B, D, E, F, and H) patients receiving placebo were also discontinued at that time. Subjects had received fewer than 12 weeks of study medication when they were discontinued. Subjects who were randomized to receive only GS-7977+RBV (Groups C & G), continued those regimens for

12 or 24 weeks as planned. Preliminary safety and efficacy data for these arms are presented below.

1.3.5.1. P2938-0721 QUANTUM Preliminary Safety

Overall, 12 subjects reported at least one Grade 2 AE and the only AE reported in > 5% of subjects included headache (n=3, 6%). No Grade 3 or 4 AEs and no SAEs were reported. The overall safety profile was consistent with that previously observed.

1.3.5.2. P2938-0721 QUANTUM Preliminary Efficacy Data

Preliminary efficacy data, available for Groups C and G, are tabulated in [Table 1-7](#).

**Table 1-7. The Proportions of Patients Achieving Viral Load Below the Lower Limit of Quantification (HCV RNA < 25 IU/mL) in Study P2938-0721**

Treatment Group	HCV Genotype	Week 4 On-Treatment	Week 4 Post-Treatment	Week 12 Post-Treatment
GS-7977+RBV for 12 weeks	GT 1	19/19 (100%)	10/19 (53%)	10/19 (53%)
	GT 2/3	6/6 (100%)	4/6 (67%)	4/6 (67%)
GS-7977+RBV for 24 weeks	GT 1	19/19 (100%)	10/19 (53%)	NAV a
	GT 2/3	6/6 (100%)	4/5 (80%) b	NAV a

a NAV: Not available, data acquisition is ongoing.

b One subject has no post-treatment data

In this study, there was no evidence of increased efficacy with prolonged treatment duration.

1.3.6. NIAID Study 11-I-0258 (IND 112,681)

Study 11-I-0258 is a randomized controlled open-label study to assess safety, tolerability and efficacy of GS-7977 400 mg QD alone or in combination with RBV to a total of 60 treatment-naïve HCV genotype 1 mono-infected individuals with less than or equal to stage 2 fibrosis. The NIAID is the sponsor of the study under IND 112,681. Subjects were enrolled into two phases to evaluate both the treatment duration as well as ribavirin dose. Phase 1 enrolled 10 subjects who were dosed with GS-7977 400 mg QD in combination with weight based RBV (1000 mg for participants weighing < 75 kg and 1200 mg for participants weighing ≥ 75kg) for 24 weeks. Upon completion of an interim safety review of these subjects at Week 12 of treatment, Phase 2 was initiated in fifty subjects. Subjects were randomized in a 1:1 ratio to receive 12 weeks of GS-7977 QD in combination with weight based RBV (1000 mg for participants weighing < 75 kg and 1200 mg for participants weighing ≥ 75kg) or 12 weeks of GS-7977 400 mg QD with low dose RBV (600mg). All subjects have been enrolled into both phases of the study. The population in Phase I was

comprised of 90% African American, 60% genotype 1a, median baseline HCV RNA log10 of 6.85 and all ≤ Stage 2 fibrosis.

#### 1.3.6.1. NIAID Study 11-I-0258 Preliminary Efficacy Data (Phase 1)

Nine out of ten subjects completed treatment through SVR 4 with one subject discontinued at Week 3 due to non-adherence. All nine subjects (100%) who completed the 24 weeks of treatment achieved SVR4 independent of race, genotype 1 subtype and IL28B genotype. Phase 2 enrollment is completed with subject treatment ongoing and will include up to 20% compensated cirrhotics.

#### 1.3.6.2. NIAID Study 11-I-0258 Preliminary Safety (Phase 1)

The interim safety analysis of these subjects at Week 12 is completed and GS-7977 was safe and well tolerated. There were no SAEs and the safety profile was consistent with that expected for RBV.

### 1.4. Overall GS-7977 SAE Summary

As of 02-Aug-2012, no serious adverse event signal has been associated with the use of GS-7977.

### 1.5. Ribavirin (RBV)

Ribavirin is a guanosine analogue that inhibits the in vitro replication of a wide range of RNA and DNA viruses {15572}, {15668}. Ribavirin monotherapy has little or no effect on the replication of HCV but can result in normalization of serum ALT activity and improvement in liver histology. When combined with interferon or PEG therapy, RBV decreases substantially the relapse rate seen after cessation of interferon therapy {12557}, {12558}.

Ribavirin is a known teratogen (FDA category X). Furthermore, RBV is known to accumulate intracellularly where it is cleared slowly, and is also excreted in semen. Therefore, extreme care must be taken to avoid pregnancy during RBV therapy and for up to 6 months following completion of treatment. A comprehensive review of RBV is contained in the package insert/SmPC.

### 1.6. Rationale for the Current Study

This is a Phase 3 open label study designed to examine the efficacy and safety of treatment with GS-7977+RBV in treatment naive or treatment experienced subjects with chronic genotype 1, 2 or 3 HCV infection who are co-infected with HIV-1.

Currently, PEG + RBV for 48 weeks is the approved standard of care for Genotype 1 patients with HIV/HCV coinfection. Response rates from large clinical trials range from 15-35% depending on various baseline predictors of response. Recent data with PEG + RBV and either TVR or BVR demonstrated improved response rates to 60-70% with 48 weeks of

treatment. Treatment naïve genotype 1 subjects receiving GS7977 + RBV in the ELECTRON, QUANTUM and NIAID (IND 112,681) studies achieved SVR4 rates ranging from 53-100% following treatment with GS-7977+RBV for 12 to 24 weeks. This range of response rates is a significant improvement over the current standard of care and is comparable to those achieved with PEG+RBV+TVR/BVR regimens while eliminating PEG and shortening duration of therapy. As patients with HIV/HCV coinfection have historically demonstrated lower response rates with treatment for HCV, GS-7977 + RBV will be administered for the longer treatment duration of 24 weeks to maximize the probability of achieving SVR with this regimen.

The response rates for the currently approved PEG+RBV for 48 weeks in treatment naïve genotype 2 and 3 patients with HIV/HCV coinfection is 60%. There are currently no approved treatments or investigational therapies for genotype 2 and 3 treatment experienced subjects with coinfection. An ongoing clinical study (P7977-0523 ELECTRON) has demonstrated that 12 weeks of treatment with GS-7977 + RBV is well tolerated and results in very high SVR rates in treatment naïve genotype 2 or 3 HCV infected subjects. Emerging data indicate that treatment of treatment-experienced genotype 2 or 3 HCV-infected subjects with GS-7977 + RBV for 12 weeks results in rapid viral clearance and a high rate of SVR, but lower than that observed in treatment naïve patients. Thus, we have again opted to utilize the longer treatment duration in these treatment-experienced patients.

The development of treatment regimen without PEG for genotype 1, 2 or 3 patients co-infected with chronic HCV infection and HIV-1 infection would allow for increased access to successful treatment to a significant proportion of the HCV-infected population. Improvements in tolerability may be expected to result in higher SVR rates if this leads to better compliance with the treatment regimen and if subjects do not require early treatment discontinuation due to safety or tolerability issues. The early viral kinetics demonstrated a similar response between HIV/HCV coinfecting and HCV monoinfected subjects, supporting the evaluation of similar regimens to those under evaluation in HCV monoinfection in other difficult to treat populations.

### **1.7. Rationale for Dose Selection of GS-7977**

[figure not shown]
The GS-7977 dose selected for further development in Phase 3 studies is 400 mg QD. This dose was associated with higher SVR rates in genotype 1 HCV infected subjects as compared to the 200 mg QD dose when given in conjunction with PEG+RBV for 24 weeks in P7977-0422. Safety and tolerability appeared similar across both dose levels and was similar to the PEG+RBV control arm. In addition, when GS-7977 400 mg QD+RBV was given to genotype 2 or 3 HCV treatment naïve infected subjects, 100% SVR24 was observed. There appears to be an advantage for the 400 mg dose based on the occurrence of viral breakthroughs in HCV genotype 1 subjects who received GS-7977 200 mg, but not in subjects who received GS-7977 400 mg in P7977-0422 (PROTON). GS-7977 400 mg with PEG+RBV is being studied in P7977-0724 (ATOMIC) which is assessing treatment durations of 12 and 24 weeks in HCV genotypes 1, 4, 5, and 6. GS-7977 400 mg is now being studied in the Phase 3 P7977-1231 (FISSION) study which is evaluating 12 week

GS-7977+RBV versus standard of care (PEG+RBV x 24 weeks) in HCV genotype 2 and 3. Additionally, GS-7977 is also being studied in the Phase 3 GS-US 334-0107 (POSITRON) study which is evaluating 12 week GS-7977+RBV versus placebo in HCV genotype 2 and 3.

Further support for the 400 mg dose can be derived from  $E_{max}$  modeling with early virologic and human exposure data which also supports the selection of a 400 mg GS-7977 dose utilizing the current 200 mg tablet formulation over others tested. Standard pharmacodynamic models were fit to individual HCV change from Baseline after three days of GS-9851 monotherapy from Study P7851-1102 and of GS-7977 monotherapy in Study P2938-0212 and various GS-9851/GS-7977 and GS-331007 steady-state pharmacokinetic parameters.

The mean GS-331007  $AUC_{tau}$  for the 400 mg dose in Study P2938-0212 is associated with approximately 77% of the maximal HCV RNA change from Baseline achievable as determined by this model, a value which is on the cusp of the plateau of the exposure-response sigmoidal curve. In a sigmoidal  $E_{max}$  model, there is a relatively linear exposure-response relationship in the 20 to 80% maximal effect range. Therefore, given that GS-7977 exposure with 200 mg tablets appears dose-proportional with single doses up to 1200 mg based upon results from QT Study P7977-0613, doses below 400 mg are expected to yield considerable reductions in the magnitude of HCV RNA change from Baseline. Similarly, in order to improve upon an efficacy prediction of 77% in the plateau of the exposure-response curve, substantial increases in exposure (and hence dose) are needed for an appreciable increase in antiviral effect (see model prediction in [\(Figure 1-3\)](#)).

**Figure 1-3. Day 3 Change from Baseline HCV RNA vs GS-331007 (PSI-6206) AUCtau during GS-7977 or GS-9851 Monotherapy**

### 1.8. Rationale for Selection of Allowed Concomitant ARV Regimens

The dose(s) of the ARV (EFV/FTC/TDF 600/200/300 mg QD, FTC/TDF 200/300 mg QD, TDF 300 mg QD, DRV/r 800/100 mg QD, RAL 400 mg BID, RPV 25 mg QD) is the recommended dose of the marketed product to be used alone or in combination with other antiretroviral agents for the treatment of HIV-1 infection in treatment naïve and/or treatment experienced subjects. GS-7977 and ARVs (EFV/FTC/TDF, ATV /r, DRV/r, RAL or RPV) are not involved in any clinically significant drug interactions (GS-US-334-0131; Section 1.3.2.1).

### **1.9. Overall Risk/Benefit Assessment**

No clinical safety issues specifically related to GS-7977 have been identified to date in HCV monoinfected or HIV/HCV coinfecting subjects. During the conduct of the study the sponsor will perform an ongoing review of safety data. An external Data Safety Monitoring Board (DSMB) will meet regularly to review safety data and to ensure subject welfare.

The expected benefits to patients being treated with GS-7977 is a rapid and durable eradication of HCV virus without the side effects associated with the use of PEG and a shortened treatment period. Potential risks include unforeseen safety issues and unknown implications of virologic failure due to the emergence of resistant virus.

For the population of HIV/HCV coinfecting subjects, the potential benefit of achieving SVR with 12 to 24 weeks of an interferon-free regimen outweighs the risks associated with the possible development of previously unidentified safety issues or the emergence of quasispecies resistant to GS-7977.

If high rates of SVR can be obtained with a shortened, interferon-free regimen, without frequent emergence of resistant HCV, the anticipated improvements in safety and tolerability would offer a favorable risk-benefit determination for individuals with chronic HCV infection who otherwise have no available treatment options.

## 2. OBJECTIVES

The primary objectives of this study are:

- To determine the efficacy of treatment with GS-7977 + RBV as measured by the proportion of subjects with sustained viral response 12 weeks after discontinuation of therapy (SVR12)
- To evaluate the safety and tolerability of GS-7977 + RBV as assessed by review of the accumulated safety data, including HIV-RNA and CD4 T-cell percent

The secondary objectives of this study are as follows:

- To determine the proportion of subjects who attain SVR at 4 and 24 weeks after discontinuation of therapy (SVR4 and SVR24)
- To evaluate the kinetics of circulating HCV RNA during treatment and after treatment discontinuation
- To evaluate the emergence of viral resistance to GS-7977 during treatment and after treatment discontinuation

The exploratory objectives of this study are:

- To identify or validate genetic markers that may predict the natural history of disease, response to therapy and/or the tolerability of medical therapies through genetic discovery research (e.g., pharmacogenomics), in subjects who provide their separate and specific consent
- To assess the effect of treatment on health related quality of life

### **3. STUDY DESIGN**

#### **3.1. Treatment Plan and Regimen**

This is an open-label study that will examine the safety, tolerability and antiviral efficacy of GS-7977 and RBV in treatment naïve and experienced subjects with chronic genotype 1, 2 or 3 HCV infection who are coinfecting with HIV-1.

A total of 230 subjects will be enrolled and treated with GS-7977 400 mg QD + RBV BID for 12 or 24 weeks based on genotype and prior treatment history. Treatment duration will be 12 weeks for Genotype 2 and 3 HCV treatment naïve subjects and 24 weeks for Genotype 1 HCV treatment naïve and Genotype 2/3 HCV treatment experienced subjects.

115 subjects with genotype 2 and 3 will be enrolled. Equal enrollment of genotype 2 versus 3 as well as treatment naïve versus treatment experienced will be targeted. An additional 115 subjects with genotype 1 will be enrolled. Approximately 20% of the entire study population may have evidence of cirrhosis at Screening.

The total time to complete all study visits is approximately 40 weeks for subjects treated with 12 weeks of therapy and 52 weeks for subjects treated with 24 weeks of therapy:

- 28 day (4 week) screening period
- 12 or 24 week treatment period
- Up to 24 week post-treatment period

#### **3.2. Visit Schedule**

All subjects will complete screening, on-treatment and post-treatment assessments. Screening assessments will be completed within 28 days of the Baseline/Day 1 visit. All subjects will complete a 4-Week Post-Treatment visit regardless of treatment duration. Subjects with HCV RNA < LLOQ at the 4-Week Post-Treatment Visit will complete 12-Week and 24-Week Post-Treatment visits unless confirmed viral relapse occurs.

The assessments performed at each visit are described in Section 6.

#### **3.3. HCV Virologic Response-Based Stopping Criteria**

Since HCV RNA will be blinded to Investigator and Sponsor except at Screening, independent monitoring will occur to assess for HCV virologic failure and the need for confirmatory HCV RNA samples. Sponsor employees involved in the virologic analysis of samples from subjects that fail to respond to treatment (virologic failures) will have access to HCV RNA data in order to identify the appropriate subject samples for virologic analyses.

The following on-treatment HCV virologic response-based treatment stopping criteria will be utilized for all subjects:

- Confirmed HCV RNA  $\geq$ LLOQ after 2 consecutive HCV RNA  $<$ LLOQ
- Confirmed  $>1$  log10 increase from nadir
- HCV RNA  $\geq$ LLOQ through 8 weeks of treatment

Confirmation should be performed as soon as possible but within 2 weeks after determination of initial observation.

### **3.4. HIV Virologic Rebound Criteria**

Subjects who meet the criteria listed below will be considered to have HIV virologic rebound:

- At any visit, have at least two consecutive plasma HIV-1 RNA levels  $\geq$  50 copies/mL (at least two weeks apart)

Following the unconfirmed HIV virologic rebound, subjects will be asked to return to the clinic for a scheduled or unscheduled blood draw for confirmation of HIV virologic rebound. If HIV virologic rebound is confirmed at the scheduled or unscheduled visit, the blood samples from this visit will be used for HIV-1 genotype/phenotype testing if the HIV-1 RNA is  $\geq$  400 copies/mL. Plasma samples with  $<$  400 copies/mL of HIV-1 RNA will not be analyzed as the protease/reverse transcriptase genotype/phenotype assays used in this study are not validated when plasma HIV-1 RNA levels are  $<$  400 copies/mL.

[figure not shown]
If greater than 20% of subjects enrolled on any specific ARV regimen experience virologic breakthrough, an ad-hoc DSMB meeting will be convened to evaluate the safety of continuing enrollment of subjects on this specific ARV therapy.

HCV medications should be continued unless safety events warrant the discontinuation of these medications, as outlined in Section 3.7 of the protocol.

These criteria only apply to subjects currently on ARV treatment and have HIV-1 RNA levels  $<$  50 copies/mL. These do not apply to subjects meeting the ARV untreated parameters outlined in the Inclusion criteria of the protocol.

Please refer to [Figure 3-1](#) for the management of subjects who meet the criteria for HIV virologic rebound.

**Figure 3-1. HIV Virologic Rebound Schema**

- a If virologic rebound is not confirmed, the subject will remain on their current ARV regimen.
- b If virologic rebound is confirmed, the HIV-1 genotype and phenotype (reverse transcriptase and protease) will be analyzed, only if the HIV-1 RNA is  $\geq 400$  copies/mL.
- c Based on the results of the genotype/phenotype assays, the subject may remain on their ARV at the discretion of the Investigator (e.g. virologic rebound due to non-adherence). If the genotyping/phenotyping assay fails to provide results, a new ARV regimen will be configured at the discretion of the Investigator.
- d A new ARV regimen will be configured, at the Investigator's discretion

### **3.5. HCV Resistance Monitoring**

Plasma samples for viral sequencing and possible phenotypic monitoring will be collected at baseline (pre-treatment) and every visit thereafter. Sequencing of the HCV NS5B-encoding region of the viral polymerase will be performed on all baseline (pre-treatment) viral samples and at any rebound time points while receiving therapy or relapse time points during off-therapy follow up where the HCV RNA  $\geq 1,000$  IU/mL.

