Large numbers of human immunodeficiency virus (HIV)-positive patients are co-infected with the hepatitis C virus (HCV) because of the shared intravenous routes of infection. Co-infection is estimated to occur in one quarter of HIV-infected persons in Europe, Australia, and the United States, and in a study from the Veterans Affairs Medical Center in Atlanta, Georgia, HCV infection occurred in as many as 33% of the patients with HIV infection {11614}. Co-infection occurs more often in those who acquired HIV through illicit IV drug abuse, which can be as high as 60%, than via men having sex with men (about 4%) {11614}. The use of antiretroviral therapy (ARV) has markedly reduced opportunistic infections and HIV-positive persons are living longer {19452}. However, liver disease has emerged as the main cause of morbidity and mortality in the HIV positive patient, and the development of end stage liver disease seems to be unrelated to the CD4 count and the immune virological status of the patient {16008}. Co-infected patients were 5 to 6 times more likely to develop decompensated liver failure and 1.5 to 2 times more likely to develop histological cirrhosis {20740}. Additionally, the risk of death in the co-infected patients was nearly 4 times greater compared with that in mono-infected individuals {20737}. Furthermore, the previous standard of care for the treatment of HCV infection, pegylated interferon alfa plus ribavirin, appears to be less effective in patients with co-infection than in patients with HCV mono-infection {10214}, {9652}, {19911}. Because end stage liver disease is the leading cause of non-AIDS-related death in the co-infected patient, there is a significant need for increased treatment options for HCV infection in this population.

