## 6. EFFICACY ANALYSES

### 6.1. Definition of the Efficacy Endpoints

The efficacy endpoints for this safety update include the following:

- SVR12 defined as HCV RNA < LLOQ (ie, < 25 IU/mL) at 12 weeks after study drug cessation for the full analysis set. The Roche COBAS® Taqman® HCV Test v2.0 for use with the High Pure System will be used to measure HCV RNA.
- Sustained virologic response 4 weeks after stopping all study drugs (SVR4) defined as HCV RNA < LLOQ (ie, < 25 IU/mL) at 4 weeks after study drug cessation for the full analysis set
- The proportion of subjects with HCV RNA below LLOQ (ie, < 25 IU/mL) while on treatment by study visit
- The proportion of subjects with on-treatment and posttreatment virologic failure, defined as the following:
  - On-treatment virologic failures
    - HCV RNA  $\geq$  25 IU/mL after having previously had HCV RNA < 25 IU/mL while on treatment, confirmed with 2 consecutive values (Note: second confirmation value can be posttreatment) or last available on-treatment measurement with no subsequent follow-up values (ie, breakthrough)
    - $>1 \log_{10}$  IU/mL increase in HCV RNA from nadir while on treatment, confirmed with 2 consecutive values (Note: second confirmation value can be posttreatment) or last available on-treatment measurement with no subsequent follow up values (ie, rebound)
    - HCV RNA persistently  $\geq$  25 IU/mL through 8 weeks of treatment (ie, nonresponse)
  - Relapse
    - HCV RNA  $\geq$  25 IU/mL during the posttreatment period having achieved HCV RNA < 25 IU/mL at end of treatment, confirmed with 2 consecutive values or last available posttreatment measurement

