### 6.2. Analysis of the Efficacy Endpoint

The efficacy endpoints will be derived for all subjects in safety analysis set using observed HCV RNA data and imputation rule specified in section 3.6.

For analyses of HCV RNA < LLOQ (ie, < 25 IU/mL) by visit while on treatment, subjects will be assigned a value at each visit based on the categorical imputation rules described in Section **Error! Reference source not found.** The 2-sided 95% exact confidence interval (CI) based on Clopper-Pearson method will be provided for the proportion {20839}. The overall category for “HCV RNA < LLOQ” will be split into the following 2 subcategories: “< LLOQ TND” for subjects with target not detected and “< LLOQ detected” for subjects with < LLOQ in tabular displays.

The point estimate of SVR4 and SVR12 rate and 2-sided 95% exact confidence interval (CI) will be provided for each treatment group and for each treatment group within each subgroup specified in section 3.4. A Forest plot will graphically present estimates and 95% confidence intervals of SVR4 and SVR12 rates for each treatment group within each subgroup.

For the SVR12 endpoint analysis, a summary table of the number and percentage of subjects with SVR12, virologic failure, and other will be created. All subjects who achieve SVR12 will be categorized as SVR12. Virologic failure will be descriptively summarized as “on-treatment virologic failure” and relapse (which will be summarized by study drug completed yes or no). Subjects who do not achieve SVR12 and do not meet criteria for virologic failure will be categorized as other. The denominator for relapse will be the number of subjects who had HCV RNA < LLOQ on their last observed on-treatment HCV RNA measurement; otherwise, the denominator will be the number of subjects in the FAS.

Details regarding SAS programming are provided in the programming specifications in **Error! Reference source not found.** of this SAP.

A data listing of HCV genotype, cirrhosis, IL28B, scheduled visit, analysis visit window, date of HCV RNA sample collection, HCV RNA load (categorical and numeric), and change from baseline for on-treatment visits will be provided for the following:

- 1), subjects with HCV virologic failure in the FAS;
- 2), all subjects in the FAS
- 3), all subjects in the safety analysis set but not in FAS

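### SAP 6.1 defines relapse by HCV RNA alone, so a new HCV infection after end-of-treatment clearance must be reported as relapse although NS5B sequences that could separate the two are already planned

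*Combined protocol and SAP*

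**What the plan says.** **Relapse.** SAP 6.1 counts as relapse an HCV RNA of 25 IU/mL or more "during the posttreatment period having achieved HCV RNA < 25 IU/mL at end of treatment, confirmed with 2 consecutive values or last available posttreatment measurement". No genotype or sequence condition is attached.

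**Outcome table.** SAP 6.2 has three outcomes: SVR12, virologic failure and other. On failure it says: "Virologic failure will be descriptively summarized as “on-treatment virologic failure” and relapse". On the residual group: "Subjects who do not achieve SVR12 and do not meet criteria for virologic failure will be categorized as other".

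**Sequencing.** Protocol 3.5 covers every pre-treatment sample ("Sequencing of the HCV NS5B-encoding region of the viral polymerase will be performed on all baseline (pre-treatment) viral samples") and "relapse time points during off-therapy follow up where the HCV RNA" is at least 1,000 IU/mL. HCV genotyping by assay is scheduled at Screening only (Protocol Appendix 2, Tables 1 to 3).

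**Resistance.** A secondary objective in Protocol 2, repeated in Protocol 9.1.1 and SAP 1.1.2, is "To evaluate the emergence of viral resistance to GS-7977 during treatment and after treatment discontinuation". The SAP contains no resistance analysis. Its only stated use of NS5B sequence is as a fallback for assigning genotype (SAP Appendix 2).

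Neither document mentions reinfection.

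**The concern.** Relapse means return of the virus that was treated. A new infection is a different event and says nothing about whether the regimen cleared the original one. RNA level cannot tell them apart; comparing the recurrent virus with the baseline virus often can, and the plan already produces both sequences for most clear-cut recurrences.

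Two things are at stake. The relapse row would carry events that are not drug failure. And a new strain can differ from the baseline strain at many NS5B positions with no selection by GS-7977, so a baseline-to-recurrence comparison without a concordance check could mistake strain differences for emergent resistance.

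Reinfection is plausible here. Protocol 1.1 attributes co-infection partly to shared intravenous routes. Exclusion 14 in Protocol 4.3 lowers the risk by excluding drug abuse within 12 months and an unexplained positive drug screen, but the urine screen is scheduled at Screening only.

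**Working it through.** **1. Follow one case through the rules.** A subject has HCV RNA below 25 IU/mL at end of treatment, acquires a new HCV strain, and has values of 25 IU/mL or more at post-treatment Week 12 and on repeat.
- SAP 6.1: the relapse definition is met, because only RNA is examined.
- SAP 6.2: the subject is not SVR12 and meets a failure criterion, so cannot be "other".
- Result: relapse, whatever the NS5B sequence shows.

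**2. Reproduce the plan's own figures** (Protocol 9.8, SAP 1.3), using half-width = 1.96 × √(p(1 − p)/n):
- n = 55, p = 0.62: 12.83 points (stated 12.8)
- n = 55, p = 0.40: 12.95 points (stated 12.9)
- n = 115, p = 0.65: 8.72 points (stated 8.7)

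These are sound and not in dispute; they supply the expected rates used below.

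**3. Expected responders and failures.** Take 115 GT1 subjects, and 115 GT2/3 subjects split equally between naive and experienced (Protocol 3.1), so 57.5 each.
- Responders: 57.5 × 0.62 + 57.5 × 0.40 + 115 × 0.65 = 133.4
- Failures: 230 − 133.4 = 96.6

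**4. Person-years to post-treatment Week 12** (84 days).
- Only expected responders at risk: 133.4 × 84/365.25 = 30.7
- All subjects at risk (upper bound): 230 × 84/365.25 = 52.9

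**5. Expected reinfections.** The documents give no incidence. Assumption: 1 to 10 per 100 person-years.
- Responders only: 30.7 × 0.01 to 30.7 × 0.10 = 0.3 to 3.1, or 0.3% to 3.2% of 96.6 failures
- All subjects: 52.9 × 0.01 to 52.9 × 0.10 = 0.5 to 5.3, or 0.5% to 5.5% of 96.6
- Chance of at least one case, responders only: 1 − exp(−0.307) = 0.26 to 1 − exp(−3.07) = 0.95

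The second line is a ceiling: it counts time in subjects who have already relapsed, for whom a further infection changes nothing. With the 55/55/115 group sizes of Protocol 9.8, expected responders are 130.8 and the first line gives 0.3 to 3.0.

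**6. Weight of one case.** 1/55 = 1.8 points; 1/115 = 0.9 points. SAP 6.2 takes as the relapse denominator those below LLOQ at the last on-treatment value, so in the relapse row one case weighs at least this much.

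**7. Bound on SVR12.** If one such subject were counted as a responder, GT2/3 naive would go from 34/55 = 61.8% (exact 95% CI 47.7 to 74.6) to 35/55 = 63.6% (49.6 to 76.2), and GT1 from 75/115 = 65.2% (55.8 to 73.9) to 76/115 = 66.1% (56.7 to 74.7). Both shifts are small beside the interval widths.

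**The case against.** The strongest reply is that this is a descriptive row with no test attached, that counting a reinfection as non-SVR12 is conservative, and that failures are listed individually with HCV RNA by visit (SAP 6.2). All of that stands. It limits the consequence but does not supply the missing rule: the listing specified in SAP 6.2 has no recurrence genotype or sequence comparison.

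Several stronger readings are tempting, and the documents do not support them.
- *Every post-treatment viraemia is called relapse.* No. SAP 6.1 requires a value below 25 IU/mL at end of treatment, and confirmation or a last available value. A post-treatment value can instead confirm an on-treatment failure.
- *Up to 9% of failures could be reinfections.* That comes from carrying the count to Week 24: (52.9 + 30.7) = 83.6 person-years gives 0.8 to 8.4 cases, divided by 96.6. The numerator and denominator do not match. The added cases arise among subjects already classed as SVR12, and SAP 3.6.1 keeps Week 24 HCV RNA out of tables and figures.
- *Most of this population acquired infection by injecting.* Protocol 1.1 says "Co-infection occurs more often in those who acquired HIV through illicit IV drug abuse, which can be as high as 60" percent. That figure is how often co-infection occurs among people who acquired HIV by injecting. It is not the injecting share of co-infected people or of trial subjects.
- *The plan counts a new strain's differences as resistance.* No passage defines an emergent-resistance comparison. This SAP covers the 120-day response and AASLD analysis only, and a separate virology plan may exist.

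The planned data also have a real limit: recurrences between 25 and 999 IU/mL are not sequenced under Protocol 3.5, so they cannot be resolved.

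**Conclusion.** The point holds. Followed exactly, SAP 6.1 and 6.2 require a reinfection after end-of-treatment clearance to be reported as relapse, although the sequences needed to recognise many such cases are already planned. This is a stated rule that yields a wrong classification. The resistance part is weaker: a missing safeguard, not a stated error.

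The likely effect is small: about 0.3 to 3 cases by post-treatment Week 12, with a ceiling of 0.5 to 5.3, against about 97 implied SVR12 failures. These counts rest on an assumed incidence of 1 to 10 per 100 person-years and on the sponsor's expected SVR12 rates. Neither the primary endpoint nor the sample size is affected.

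The rule should still be fixed in advance. The study is open-label and uncontrolled, and any later decision that a recurrence was really a reinfection would lower the reported relapse rate.

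**What to change.** Add to SAP 6.1 and 6.2:
- Where a post-treatment recurrence has been sequenced under Protocol 3.5 (HCV RNA at least 1,000 IU/mL), report the subject as reinfection, in a separate row of the virologic outcome table and not as relapse, if the NS5B sequence shows a genotype or subtype different from baseline, or does not cluster with the subject's own baseline sequence in a phylogenetic analysis whose method and threshold are stated beforehand.
- Recurrences that are not sequenced remain relapse. A footnote should say so and give their number.
- Exclude discordant sequences from any emergent-resistance count, here and in any virology plan.
- Keep reinfected subjects as non-SVR12 in the primary analysis. A sensitivity SVR12 without them is optional and should be labelled as able only to raise the rate.

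The cost is SAP wording and an analysis of sequences already planned. No extra samples, visits or subjects are needed. Protocol 3.3 already gives the sponsor's virology staff access to HCV RNA data to select failure samples, so no wider unblinding is required. The remaining weakness is that low-level recurrences default to relapse.
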